## **5.2 Secondary Endpoints**

A secondary endpoints will be the difference in message effectiveness between the video with versus without the inclusion appeal, evaluated using a 6-question survey adopted from KC Davis and colleagues.

## **5.3 Statistical Methods**

### **5.3.1 Baseline Data**

Baseline and demographic characteristics will be summarized by standard descriptive summaries (e.g. means and standard deviations for continuous variables such as age and percentages for categorical variables such as gender).

### **5.3.2 Efficacy Analysis**

For our assessment of differences between the three groups' intent to enroll, we will use a series of one-way between-group analyses of variance to determine the impact of the experimental video vs. control video vs. no video on enrollment intent.

## **5.4 Sample Size and Power**

Based on data from two similar studies in adults we will need approximately 20 completed surveys per group to have 80% power to detect a difference with a 0.05 significance level. Because our plan is to conduct the study before or after scheduled clinic visits, where illness, weather and transportation may impact a family's ability to complete the study, we plan to enroll 90 patients to account for this attrition.

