### Setting/Participants:

Phase 1 involves parents from the CHOP Research Family Partners and utilizes consensus/voting to review study design and materials. Phase 2 takes place in the CHOP primary care waiting rooms. Ninety parents who self-identify as English-speaking African/African American adults will be enrolled.

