### 2.1 Primary Objective (or Aim)

The primary objective is to compare intent to enroll in a research discovery site after seeing a video with an inclusion appeal versus one without such an appeal—focusing on parents and guardians who identify as African or African American.

---

 Jeannine S. Skinner et al., “The Impact of an Educational Video on Clinical Trial Enrollment and Knowledge in Ethnic Minorities: A Randomized Control Trial,” *Frontiers in Public Health* 7 (2019): 104, <https://doi.org/10.3389/fpubh.2019.00104>.

 Joseph Petraglia, “The Importance of Being Authentic: Persuasion, Narration, and Dialogue in Health Communication and Education,” *Health Communication* 24, no. 2 (March 2009): 176–85, <https://doi.org/10.1080/10410230802676771>.

 Melanie B. Tannenbaum et al., “Appealing to Fear: A Meta-Analysis of Fear Appeal Effectiveness and Theories,” *Psychological Bulletin* 141, no. 6 (November 2015): 1178–1204, <https://doi.org/10.1037/a0039729>.

 Graton Aurélien and Mailliez Melody, “A Theory of Guilt Appeals: A Review Showing the Importance of Investigating Cognitive Processes as Mediators between Emotion and Behavior,” *Behavioral Sciences (Basel, Switzerland)* 9, no. 12 (November 20, 2019): E117, <https://doi.org/10.3390/bs9120117>.

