planning to invite participants to complete the study at a Penn or CHOP facility, rather than at home. Study participants will complete materials using an online survey completion and video display system (REDCap or Qualtrics). Each participant will complete questions about their age, gender identity, race/ethnicity, education attainment, and their child's age and gender identity. We will then ask a subset of questions from the NIH Health Information National Trends Survey to assess clinical trials knowledge. After these questions, all eligible participants will be randomly show either one of two videos (with or without the inclusion appeal) followed by a short survey about perceived effectiveness of the message or taken directly to the final question. The final question will ask if they are willing to receive messages about potential clinical trials for their child. If they select yes, they will be taken to the enrollment screen for the registry above and will be given assistance by the research coordinator to help them complete the process if required.

Each participant will be paid \$20 for participating in the study. The primary outcome will be intention to join a research registry called the Research Discovery Finder that notifies parents about research studies. We will measure attempts to join, rather than joining, in case the process of joining is too complicated or confusing. Based on data from two similar studies in adults we will need approximately 30 completed surveys per group to have 80% power to detect a difference with a 0.05 significance level. Results will be reported using standard descriptive statistics. Between group differences in intent to enroll will be analyzed using chi-square analysis, with significance set at the 0.05 level. We will use a series of one-way between-group analyses of variance to determine the impact of the experimental video on dependent variables.

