### **3.1.4 Total Number of Study Sites/Total Number of Subjects Projected**

The study will be conducted at one site in the Philadelphia area.

It is expected that approximately 100 subjects will be enrolled to produce 90 evaluable subjects. The study enrollment is planned to conclude in October 2022.

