# **5 STATISTICAL CONSIDERATIONS**

## **5.1 Primary Endpoint**

The primary endpoint will be the difference in intent to enroll between the three groups.

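### The plan gives both 20 and 30 completed surveys per group for the same 80% power with no effect stated, and uses 90 both as the enrolled and as the evaluable number

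*Combined protocol and SAP*

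**What the plan says.** Two sections state the sample size requirement. Section 3.1.1 (Trial) says "we will need approximately 30 completed surveys per group to have 80% power to detect a difference with a 0.05 significance level". Section 5.4 (Sample Size and Power) says "we will need approximately 20 completed surveys per group to have 80% power to detect a difference with a 0.05 significance level". Both rest the number on two similar studies in adults. Neither states the size of the difference, the expected proportions, the sidedness, the comparison or the test.

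Three places give enrolment:
- Abstract, Setting/Participants: "Ninety parents who self-identify as English-speaking African/African American adults will be enrolled".
- Section 5.4, after noting that illness, weather and transport may prevent completion: "we plan to enroll 90 patients to account for this attrition".
- Section 3.1.4: "It is expected that approximately 100 subjects will be enrolled to produce 90 evaluable subjects".

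The rest of the plan does not show what is being powered. Section 2.1 sets out to "compare intent to enroll in a research discovery site after seeing a video with an inclusion appeal versus one without such an appeal", which is a two-arm contrast. Section 5.1 says "The primary endpoint will be the difference in intent to enroll between the three groups". Section 3.1.1 says "Between group differences in intent to enroll will be analyzed using chi-square analysis, with significance set at the 0.05 level", whereas section 5.3.2 assigns the same outcome to one-way analyses of variance.

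**The concern.** The two power statements agree on everything they disclose (basis, power, significance level, unit of count) and differ by half in the result: 3 × 20 = 60 completers against 3 × 30 = 90. Both count completed surveys, so 30 cannot be read as the enrolled counterpart of 20.

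The number 90 also changes meaning. In section 5.4 it is the enrolled number, from which losses are expected. In section 3.1.4 it is what remains after losses. The abstract gives 90 as enrolled and does not mention attrition.

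A study team could therefore stop at 60 completers, at 90 enrolled or at about 100 enrolled and cite the protocol each time. If 30 per group is the real requirement, stopping at 60 completers leaves the study well short of its stated power, and a null result could be misread as evidence that the appeal does not work. With no effect or test stated, the 80% claim cannot be checked at either size.

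**Working it through.** **Inputs from the plan.** Three arms; 80% power; level 0.05; 20 per group (5.4) or 30 per group (3.1.1); 90 enrolled (abstract, 5.4) or about 100 enrolled for 90 evaluable (3.1.4).

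**Assumed here because the plan is silent.** Two-sided testing, equal groups, comparator rates of 10% to 50%, and, for one scenario, a 10% loss applied to 90 enrolled.

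**1. The plan's own figures.** Neither 20 nor 30 can be reproduced without an effect. Unstated choices move the answer across that range. For an illustrative 30% vs 70%, the two-proportion formula gives these numbers per group:

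| | Uncorrected | Continuity-corrected |
|---|---|---|
| One-sided | 19 | 23 |
| Two-sided | 24 | 29 |

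The plan does not say that its two figures differ in this way.

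**2. Attrition implied by each section.**
- Section 5.4: 1 − 60/90 = 33.3%.
- Section 3.1.4: 1 − 90/100 = 10%.
- To end with 90 completers, one must enrol 90/0.90 = 100 at 10% loss, or 90/(2/3) = 135 at 33.3% loss.
- If 90 are enrolled and 10% are lost: 90 × 0.90 = 81, or 27 per group.

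**3. Can 20 and 30 both give 80%?** For two proportions with n per group,

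power = Φ[(d√n − 1.96·s₀)/s₁], where s₀ = √(2p̄(1−p̄)) and s₁ = √(p₁(1−p₁) + p₂(1−p₂)).

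Take p₁ = 30% and p₂ = 65.43%, so d = 0.3543, s₀ = 0.7064, s₁ = 0.6604 and 1.96·s₀ = 1.3845.
- n = 30: (1.9406 − 1.3845)/0.6604 = 0.842, power 80%.
- n = 27: (1.8410 − 1.3845)/0.6604 = 0.691, power 75.5%.
- n = 20: (1.5845 − 1.3845)/0.6604 = 0.303, power 61.9%.

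In the other direction, the difference with 80% power at 20 per group has 93.6% at 30. These powers are the same at all five assumed rates.

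**4. The three-group tests show the same pattern.** f and w are the standardised effects with 80% power at each total.

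| Test | 90 total | 81 total | 60 total | Power at 81, effect set at 90 | Power at 60, effect set at 90 | Power at 90, effect set at 60 |
|---|---|---|---|---|---|---|
| One-way ANOVA | f = 0.333 | f = 0.352 | f = 0.411 | 75.2% | 60.7% | 94.0% |
| Chi-square, 2 df | w = 0.327 | w = 0.345 | w = 0.401 | 75.4% | 61.5% | 93.6% |

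**5. Detectable difference, appeal video vs no-appeal video** (percentage points, 80% power, two-sided 0.05).

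| Per group | Test | 10% | 20% | 30% | 40% | 50% |
|---|---|---|---|---|---|---|
| 30 | Uncorrected | 30.9 | 34.3 | 35.4 | 35.1 | 33.4 |
| 27 | Uncorrected | 32.9 | 36.2 | 37.3 | 36.8 | 34.9 |
| 20 | Uncorrected | 39.3 | 42.3 | 43.0 | 42.0 | 39.5 |
| 30 | Corrected | 33.6 | 37.6 | 38.3 | 37.9 | 35.7 |
| 27 | Corrected | 36.3 | 39.9 | 41.5 | 39.9 | 37.3 |
| 20 | Corrected | 43.7 | 48.3 | 48.6 | 46.1 | 42.1 |
| 20 | Fisher | 42.8 | 47.3 | 47.9 | 45.1 | 41.8 |

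Columns are assumed rates in the no-appeal arm. Uncorrected rows use the formula in step 3. Corrected and Fisher rows come from exact binomial enumeration; Fisher equals the corrected test at 27 and 30.

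**The case against.** No sum in the plan is wrong taken alone. Section 5.4 is coherent by itself (60 completers, 90 enrolled), and 3.1.1 and 3.1.4 fit each other (90 completers, about 100 enrolled). On this view the document holds two unreconciled plans, and different unstated choices of sidedness or correction could yield about 20 and about 30 from one effect. It is true that neither number is shown to be wrong in itself. But nothing in the text signals two different calculations.

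The 27-per-group scenario combines a requirement from 3.1.1, an enrolment from 5.4 and a loss rate that matches only 3.1.4. That is a fair description, and the scenario is an illustration. Small losses cost little: 29 per group still gives about 79% where 30 gives 80%, and both statements say approximately.

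The 100 in section 3.1.4 might include the up to 9 Phase 1 parents of section 7.5 (9 + 90 = 99). Even so, 3.1.4 would have 90 evaluable while 5.4 expects losses from 90 enrolled.

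The assumed rates stop at 50%. At 70%, the uncorrected difference at 30 per group falls to 26.5 points, and at 20 per group no difference reaches 80% power. The point ranges therefore depend on the assumption; the contradiction does not.

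This is a minimal-risk, one-visit pilot, which lowers the stakes. It still claims 80% power and tests at 0.05, so the claim should be checkable.

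**Conclusion.** The concern holds. Sections 3.1.1 and 5.4 are both current text and give incompatible requirements on one stated basis, and 90 cannot be both the enrolled number with losses expected and the number left after losses. At least one of the stated sample size figures needs correcting; the documents do not show which.

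The gap matters. Under any single two-sided test examined, 80% power at one size means about 61–62% or about 94% at the other. That result does not depend on the assumed rates. The shortfall to about 75% at 27 per group depends on 30 being the requirement and on a 10% loss from 90 enrolled. The detectable differences for the video contrast, about 31 to 35 points at 30 per group and 39 to 43 at 20, depend on comparator rates of 10% to 50% and an uncorrected test; corrected or Fisher tests need roughly 34 to 38 and 42 to 49. These are large differences for a study of this size to rely on.

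**What to change.** Choose one number of completers per group, one enrolment total and one attrition rate. Say whether 90 is enrolled or evaluable, and use the same figures in the abstract and in sections 3.1.1, 3.1.4 and 5.4. If Phase 1 parents are counted in any total, say so.

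Replace the unspecified difference in both power statements with one text, for example:

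> We will enrol [total] parents in Phase 2; with an expected loss of [x]%, this gives [n] completers per group. For [contrast], a two-sided [named test] at 0.05 has 80% power to detect a difference of [d] percentage points, assuming a rate of [p] in [named comparator arm].

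For the two-video contrast, take [d] from the table row for the chosen n and test, and label [p] as an assumption. If the three-group comparison is chosen instead, one difference is not enough: state the three assumed rates and the resulting w, where w² is the average of (pᵢ − p̄)² over the arms divided by p̄(1 − p̄), and compare it with the values in step 4. If the expected completers fall short of the stated requirement, report the power at that number, such as about 75% at 27 when 30 is required.

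The cost is wording in four places, with no change to procedures. Keeping 90 enrolled needs no extra participants; adopting about 100 raises the total in the abstract and 5.4 but not in 3.1.4. The plan will then show openly that only a large difference is detectable with 80% power.

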## **5.5 Interim Analysis**

Interim analysis will not be necessary for this pilot study.

## **6 SAFETY MANAGEMENT**

Since the study procedures are not greater than minimal risk, SAEs are not expected. If any unanticipated problems related to the research involving risks to subjects or others happen during the course of this study (including SAEs) they will be reported to the IRB in accordance with CHOP IRB SOP 408: Unanticipated Problems Involving Risks to Subjects. AEs that do not meet prompt reporting requirements will be summarized in narrative or other format and submitted to the IRB at the time of continuing review (if continuing reviews are required), or will be tracked and documented internally by the study team but not submitted to the IRB (if continuing reviews are not required).

### **6.1 Definition of an Adverse Event**

An adverse event is any untoward medical occurrence in a subject who has received an intervention (drug, biologic, or other intervention). The occurrence does not necessarily have to have a causal relationship with the treatment. An AE can therefore be any unfavorable or unintended sign (including an abnormal laboratory finding, for example), symptom, or disease temporally associated with the use of a medicinal product, whether or not considered related to the medicinal product.

All AEs (including serious AEs) will be noted in the study records and on the case report form with a full description including the nature, date and time of onset, determination of non-serious versus serious, intensity (mild, moderate, severe), duration, causality, and outcome of the event.

## **6.2 Definition of a Serious Adverse Event (SAE)**

An SAE is any adverse drug experience occurring at any dose that results in any of the following outcomes:

- death,
- a life-threatening event (at risk of death at the time of the event),
- requires inpatient hospitalization or prolongation of existing hospitalization,
- a persistent or significant disability/incapacity, or
- a congenital anomaly/birth defect in the offspring of a subject.

Important medical events that may not result in death, be life-threatening, or require hospitalization may be considered a serious adverse drug event when, based upon appropriate medical judgment, they may jeopardize the subject and may require medical or surgical intervention to prevent one of the outcomes listed in this definition.

A distinction should be drawn between serious and severe AEs. A severe AE is a major event of its type. A severe AE does not necessarily need to be considered serious. For example, nausea which persists for several hours may be considered severe nausea, but would not be an SAE. On the other hand, a stroke that results in only a limited degree of disability may be considered a mild stroke, but would be an SAE.

### **6.2.1 Relationship of SAE to study drug or other intervention**

The relationship of each SAE to the study intervention should be characterized using one of the following terms in accordance with CHOP IRB Guidelines: definitely, probably, possibly, unlikely or unrelated.

## **6.3 IRB/IEC Notification of SAEs and Other Unanticipated Problems**

The Investigator will promptly notify the IRB of all on-site unanticipated, serious Adverse Events that are related to the research activity. Other unanticipated problems related to the research involving risk to subjects or others will also be reported promptly. Written reports will be filed using the eIRB system and in accordance with the timeline below. External SAEs that are both unexpected and related to the study intervention will be reported promptly after the investigator receives the report.

Type of Unanticipated Problem	Initial Notification (Phone, Email, Fax)	Written Report
Internal (on-site) SAEs Death or Life Threatening	24 hours	Within 2 calendar days

Internal (on-site) SAEs All other SAEs	7 days	Within 7 business days
Unanticipated Problems Related to Research	7 days	Within 7 business days
All other AEs	N/A	Brief Summary of important AEs may be reported at time of continuing review

### **6.3.1 Follow-up report**

If an SAE has not resolved at the time of the initial report and new information arises that changes the investigator's assessment of the event, a follow-up report including all relevant new or reassessed information (e.g., concomitant medication, medical history) should be submitted to the IRB. The investigator is responsible for ensuring that all SAE are followed until either resolved or stable.

## **7 STUDY ADMINISTRATION**

### **7.1 Treatment Assignment Methods**

#### **7.1.1 Randomizations**

One of three arms will be randomly presented to each participant through a specialized survey flow. Participants will then be administered one of three arms through a web-based randomizer. This data will be recorded and stored in Qualtrics.

#### **7.1.2 Blinding**

No blinding will be required.

#### **7.1.3 Unblinding**

N/A

### **7.2 Data Collection and Management**

All data and records will be kept confidential and stored in Qualtrics

All data will be backed up in a password protected file in Box, and will be analyzed using Excel and R.

### **7.3 Confidentiality**

All data and records generated during this study will be kept confidential in accordance with Institutional policies and HIPAA on subject privacy.

No identifiable data will be used for future study without first obtaining IRB approval or determination of exemption. The investigator will obtain a data use agreement between the provider (the PI) of the data and any recipient researchers (including others at CHOP) before sharing a limited dataset (PHI limited to dates and zip codes).

### **7.4 Regulatory and Ethical Considerations**

#### **7.4.1 Data and Safety Monitoring Plan**

The CHOP PI will monitor and review the study progress, subject safety, and the accuracy and security of the emerging data.

#### **7.4.2 Risk Assessment**

This study, which does not directly involve children, and which consists only of surveys conducted during a pre-scheduled clinic visit, qualifies as a minimal risk study.

#### **7.4.3 Potential Benefits of Trial Participation**

This study does not confer direct benefits (other than compensation) to participants.

#### **7.4.4 Risk-Benefit Assessment**

This study which has essentially no risk and a very small monetary benefit is justifiably more benefit than risk.

#### **7.5 Recruitment Strategy**

Participants in the first phase of the study will be selected from families already signed up for the Research Family Partners program at CHOP. We are selecting no more than 9 parents from this group to advise us on study design, video development, message effectiveness and targetedness. Meetings will be using teleconferencing software.

Participants in the second phase will be invited to participate based on a review of the scheduled visits to the selected primary care sites each week. We will complete the study procedures in the waiting room or exam room before the visit (depending on the staffing and clinic flow, determined by asking the nurse manager each day we are in the clinic), and asking them to meet with us at the conclusion of the visit to complete the study if they are eligible and we were unable to complete the study initially. We do not anticipate requiring advertising.

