## **4.1 Visit 1 (Phase 2)**

Detailed description of study visit including all procedures.

Potential participants will be invited to enroll in the study based on scheduled information and self-identified race/ethnicity.

Upon arrival to clinic, potential participants will complete a brief screening form related to the inclusion criteria (English proficiency, able to watch a video or see an image, African/African American race). If inclusion criteria are met, they will receive informed consent form (with review and discussion) and be asked to sign it.

Participants will complete an online survey containing: (1) demographic questions (their age, gender identity, education attainment, and their child's age and gender identity); (2) clinical trials knowledge, using a subset of questions from the NIH Health Information National Trends survey

Participants will be randomly shown either: (1) one of two videos (with or without the inclusion appeal) followed by a short survey about perceived effectiveness of the message; or (2) a paragraph and image describing the CHOP Research Discovery Finder.

Participants will be asked if they are willing to receive messages about potential clinical trials for their child from the CHOP Research Discovery Finder. If they select yes, they will be taken to the enrollment screen for the registry above and will be given assistance by the research coordinator to help them complete the process if required.

Each participant will be paid \$20 for participating in the study.

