#### **7.6 Informed Consent/Accent and HIPAA Authorization**

Members of the research team will review the study and obtain informed consent. No additional HIPAA authorization is required. Once a family member has agreed to participate, she will be given an iPad that displays a survey that already contains the patient's research ID. We will ask screening questions at that time. Parents/guardians who screen as eligible for the study will be invited to continue in the study after the visit. Surveys will be completed using researcher-provided iPads, and will be completed in the waiting room. Privacy will be assured through the use of headphones during the time the video is playing, and through the use of an iPad to collect the information.

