##### **7.6.2 Main Study**

A research coordinator (RC) will screen...

The RC will screen patients while awaiting the start of their visit and then check for their eligibility. Once it is determined that they are interested in participating in the study. We will consent them, review their eligibility, and use Qualtrics randomization tool to assign the participant to one of the three arms.

No HIPAA authorization form will be needed for this study.

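### The timing rules allow a clinic visit to fall between random assignment and the outcome question, so completion could differ by arm; any pause should come before the randomiser

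*Combined protocol and SAP*

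**What the plan says.** The combined protocol and SAP describes the timing of Phase 2 in several places.

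- Section 7.5 sets the default: "We will complete the study procedures in the waiting room or exam room before the visit". If that fails, parents are to be met "at the conclusion of the visit to complete the study if they are eligible and we were unable to complete the study initially".
- Section 7.6 has a different sequence: "Parents/guardians who screen as eligible for the study will be invited to continue in the study after the visit".
- Section 5.4 allows either: "our plan is to conduct the study before or after scheduled clinic visits".
- Section 7.6.2 says "The RC will screen patients while awaiting the start of their visit and then check for their eligibility". Consent, eligibility review and assignment in Qualtrics follow, with no stated timing.
- The schedule of procedures lists randomisation in the screening column. The survey, with any video embedded, and the registry question are in the intervention column.

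Sections 3.1.1 and 4.1 (Phase 2) show the assigned material after the demographic and trial-knowledge questions, and the registry question comes last. Under section 4.1 (Phase 2), the video arms get "one of two videos (with or without the inclusion appeal) followed by a short survey about perceived effectiveness of the message". The third arm gets a paragraph and image, or, in section 3.1.1, goes straight to the last question.

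The plan expects incomplete sessions. Section 5.4 refers to clinic conditions "where illness, weather and transportation may impact a family's ability to complete the study", and section 3.1.4 expects that "approximately 100 subjects will be enrolled to produce 90 evaluable subjects". The early termination section foresees parents stopping mid-survey for lack of time and pays them in full.

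**The concern.** In section 7.5, finishing a study that could not be completed at first implies a session already begun, and nothing limits where the break may fall. A parent could be assigned, watch the video, be called in to see the clinician, and be asked the registry question only on return, or never.

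Two things are at stake. First, the video arms have more to get through before the outcome, so they have more chance of being interrupted. If parents who do not return differ in intent from those who do, unequal loss after randomisation biases a comparison of completers. Second, for parents who do return, a clinic visit lies between exposure and outcome. It could dilute or alter the response to a short message, and nothing requires the timing to be recorded.

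**Working it through.** **1. Where the break could fall**

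| Source | Sequence | Position of a break |
|---|---|---|
| 5.4 | before or after the visit | not addressed |
| 7.5 | before; finish afterwards if incomplete | anywhere, including after assignment or after the video |
| 7.6 | screen, then continue after the visit | before the survey and exposure |
| 7.6.2 | screening during the wait; assignment untimed | not fixed |
| Schedule | randomisation listed with screening | a pause after screening would follow assignment |

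Only section 7.6 points to a break before exposure. Even that break would follow assignment if the schedule is taken literally.

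**2. Steps between assigned material and outcome**

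- Appeal video: informational video with the added appeal segment (section 1.2), then the six-question survey (section 5.2).
- Plain video: the same without the segment.
- No video: a paragraph and image, or nothing.

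Running times are not given. The contrast in exposure to interruption is large between video and no video, and small between the two videos.

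**3. The plan's own loss figures**

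- Section 5.4: 20 completed × 3 groups = 60, with 90 enrolled. Implied loss is 1 − 60/90 = 33%.
- Section 3.1.4: 100 enrolled for 90 evaluable. Implied loss is 1 − 90/100 = 10%.

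Neither figure is split by arm, or into loss before and after randomisation.

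**4. Size of a possible bias**

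Let p be true intent, equal in both arms; L the loss in an arm; and q the intent among those lost, taken as the same in both arms. Among completers,

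observed rate = (p − L·q)/(1 − L).

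Assumed, not from the documents: p = 0.50; L = 0.20 in a video arm and 0.05 with no video; 30 randomised per arm. Over two video arms and one other, average loss is (20 + 20 + 5)/3 = 15%, between the plan's 10% and 33%.

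- q = 0.25 (half the average): (0.50 − 0.05)/0.80 = 56.3% against (0.50 − 0.0125)/0.95 = 51.3%. Difference 4.9 points.
- q = 0: 0.50/0.80 = 62.5% against 0.50/0.95 = 52.6%. Difference 9.9 points.
- q = 0.50 (loss unrelated to intent): 50% against 50%. Difference 0.
- Equal L in both arms: difference 0 for any q.

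For the two-sided 5% test, the standard error with 24 and 28.5 completers is √[0.25 × (1/24 + 1/28.5)] = 0.139. The type I error becomes about 6.5% in the first case and 11% in the second.

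With the same losses and q from half the average down to zero, the difference is 3.0 to 5.9 points at p = 0.30 and 6.9 to 13.8 points at p = 0.70.

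**5. Counting missing outcomes as no**

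With the same losses, unrelated to intent: 0.50 × 0.80 = 40% against 0.50 × 0.95 = 47.5%. That is a spurious 7.5 points against video, so this rule is not a safe primary analysis.

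**The case against.** The strongest reply is that no section places the visit between video and outcome. Section 7.5 can be read in line with 7.6, with parents screened beforehand and everything else done afterwards. Section 7.6.2 ties only screening to the wait. Sections 3.1.1 and 4.1 (Phase 2) reveal the arm after the baseline questions, so some interruptions would come before the arm could matter. This stands as a plausible reading, but no section says that it governs, and section 7.5 and the schedule allow the other.

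The causes of attrition named in section 5.4 have no evident link to arm, and no section specifies an analysis of completers only. Both points stand. A reader might infer that interrupted parents will be dropped, but the documents do not say how they are counted. Lack of time, however, is foreseen as a reason for stopping, and it bears more on arms with more steps.

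The objective in section 2.1 compares the two videos, where loss should be similar. This also stands, but the endpoint in section 5.1 covers all three groups, so the no-video comparison is part of the primary result.

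**Conclusion.** The timing passages conflict and, read together, permit a break after assignment or after exposure. Arm-related loss is then a risk, mainly for video against no video and much less for appeal against no appeal. For parents who return, an unrecorded clinic visit may separate exposure from outcome.

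The size is unknown. About 5 to 10 points is an illustration that needs 50% true intent, losses of 20% and 5%, lower intent among those lost, and a comparison of completers only. Under equal loss, or loss unrelated to intent, it is zero.

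A reader might infer that the plan sends parents to the visit between video and question, or that the appeal comparison is biased by this amount. The documents support neither: the first is allowed but not stated, and the figures concern a different contrast. The change is worth making because it costs little, and an outcome lost after randomisation cannot be recovered later.

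**What to change.** Reconcile sections 5.4, 7.5, 7.6 and 7.6.2 and the schedule of procedures to one rule. Screening, consent and baseline questions may be done before the visit. The randomiser is launched only when the video or paragraph, the effectiveness survey where it applies, and the final question can be finished in one sitting. Otherwise the pause comes before randomisation, and the parent is randomised on return.

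Record whether completion was before or after the visit, and report numbers randomised and completed by arm. Use counting missing outcomes as no only as a sensitivity analysis.

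The cost is protocol wording, a survey page before the randomiser offering to continue now or after the visit, and one extra data field. The downside is that some families who do not return are lost before randomisation instead of after it. That reduces numbers but does not disturb the balance between arms.
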